Cross-sectional mediation. Basic cross-sectional mediation analyses typically involve three regressions: the mediator is regressed on the predictor (the 'a' path), and the outcome is regressed on both the mediator (the 'b' path) and the predictor (the 'c' path or total effect of the predictor on the outcome). The total effect of the predictor on the outcome is then split into the indirect effect, which describes what part of the total effect goes through the mediator (calculated as a*b), and the direct effect, which describes what part of the total effect is independent of the mediator. While early methods for mediation involved the fitting of separate multiple regression models, more modern methods employ structural equation modeling to fit all model parameters simultaneously. This allows for more rigorous testing of indirect effects, including more accurate standard errors and improved missing data handling.

Longitudinal mediation. An important part of mediational tests is the passage of time, as predictors must precede the variables they cause. As such, mediation models have been extended into longitudinal modeling (as shown in Figure 3). This model extends the cross-lagged panel design model, such that both the 'a' path (from the predictor to the mediator) and the 'b' path (from the mediator to the outcome) span one lag (e.g., from age 13 months to 14 months, from 14 months to 15 months, etc.), while the direct effect of the predictor on the outcome (the 'c' path) spans two lags (e.g., from age 13 months to 15 months, 14 months to 16 months, etc.). The inclusion of these time lags allow for the use of all measurement occasions simultaneously while also ensuring that the effects required in any mediation analysis show the temporal ordering to test causal direction. As with all other analyses, we will include relevant covariates in all steps of both the cross-sectional and longitudinal mediation models.

Timing of effects and extensions of longitudinal mediation. Longitudinal mediation models provide many benefits over cross-sectional mediation, but a weakness of this approach is that it is tied to the lags inherent to our study design. The intervention predicts growth in child communication skills, which we assess monthly for longitudinal modeling. However, children may develop either more quickly or more slowly than this monthly interval, which is not traditionally accounted for in longitudinal mediation analyses.

[figure not shown]

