Modern extensions of longitudinal mediation utilize the benefits of these approaches with a more continuous approach to lags. DeBoeck & Preacher's (2016)92 continuous time longitudinal mediation model merges existing longitudinal mediation methods with dynamical systems modeling to estimate not only the size of the mediational paths, but also the optimal lag for each parameter. We hypothesize that intervention effects on parent use of communication support strategies will occur relatively quickly, while the effects on child

outcomes will develop more slowly over

time.

Latent Growth Curves and Autoregressive Latent Trajectories. The above mediation models provide ways of testing our primary hypotheses, but also allows us to test secondary questions about the shape and timing of change in all studied constructs. Latent growth curve models specify that change in a measured variable can be modeled via latent variables representing initial level and change, each of which are free to vary across individuals.

The Autoregressive Latent Trajectories model (ALT93) is the combination of a latent growth curve and a cross-lagged regression model (Figure 3) which is commonly used in longitudinal mediation.

Specifically, this model takes a bivariate growth curve model of parent and child language behaviors and adds autoregressions (such that parent use of communication support strategies at early time points predicts later parent use of communication support strategies, see the "alpha" parameters) and cross-regression (such that earlier parent use of communication support strategies predict later child communication skills, see the "beta" parameters). Use of the ALT model will allow improved model fit and greater accuracy in specifying the longitudinal trends in both parent behaviors and child language outcomes.

These growth curves will further allow a merging of the cross-sectional and longitudinal mediation paradigms described above. Analyses 4.1a and 4.2a use growth in child communication skills as an outcome, while analysis 4.3a uses different growth curves as mediators and outcomes, respectively. These approaches will use basic cross-sectional methods with single variables representing the predictor, mediator, and outcome. However, the mediators and outcomes in these models will be latent variables that are estimated within a latent growth curve model.

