Aim 4 analytic plan. All models in this section will utilize SEM for estimation. Indirect effects will be defined as the product term of the intervention to mediator and mediator to outcome regressions, and the standard error and significance tests for this indirect effect will be estimated directly via likelihood-based confidence intervals rather than traditional multiple step methods (e.g., Sobel method⁹⁴).

Analysis 4.1a. Intervention will predict a latent variable that describes overall parent use of communication support strategies from a parent-child interaction measured monthly from 12 months (pre) to 18 months of age (post). This latent parent variable will in turn predict the slope term from a latent growth curve of number of child prelinguistic communicative acts from a language sample measured monthly from 12 months (pre) to 18 months (post). This model will include simultaneous estimation of the intervention effect, parent use of a communication support strategy latent variable, and a child prelinquistic communicative acts latent growth curve model.

Analysis 4.1b. Intervention will predict a latent variable that describes overall parent use of communication support strategies from a parent-child interaction measured monthly from ages 12 months (pre) to 18 months of age (post). This latent parent strategy variable will in turn predict CSBS Total Scaled scores at 18 months of age (post).

Analysis 4.2a. Intervention will predict a latent variable that describes overall parent use of communication support strategies from a parent-child interaction measured monthly from 18 months (post) to 36 months of age (follow-up). This parent variable will in turn predict the slope term from a latent growth curve of spoken words (latent variable from MCDI Words Said and number of different words from a language sample) from 18 months (post) to 36 months of age (follow-up). This model will include simultaneous estimation of the intervention effect, a parent use of communication support strategy latent variable, and a child spoken words latent growth curve model.

Analysis 4.2b. Intervention will predict a latent variable that describes overall parent use of communication support strategies from a parent-child interaction measured monthly from ages 18 months (post) to 36 months of age (follow-up). This latent parent strategy variable will in turn predict PLS-5 Total Standard Scores at 36 months of age (follow-up).

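### Mediation analyses 4.1a and 4.2a take mediator and outcome from the same months, and 4.1b and 4.2b run the mediator up to the outcome date, so child influence on parents could be read as mediation

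*SAP*

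**What the plan says.** Under Longitudinal mediation, the SAP states that "predictors must precede the variables they cause" and describes a cross-lagged model in which the paths into and out of the mediator each span one month. The next two subsections add a continuous-time version and the Autoregressive Latent Trajectories (ALT) model.

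The numbered analyses in the Aim 4 analytic plan are built differently. In 4.1a the parent factor comes "from a parent-child interaction measured monthly from 12 months (pre) to 18 months of age (post). This latent parent variable will in turn predict" the child's slope over those same months. In 4.2a it comes "from a parent-child interaction measured monthly from 18 months (post) to 36 months of age (follow-up). This parent variable will in turn predict" the slope of "spoken words (latent variable from MCDI Words Said and number of different words from a language sample) from 18 months (post) to 36 months". In 4.1b and 4.2b the same two parent factors predict one score each: CSBS at 18 months and PLS-5 at 36 months.

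The subsection on latent growth curves and ALT says of 4.1a, 4.2a and 4.3a: "These approaches will use basic cross-sectional methods with single variables representing the predictor, mediator, and outcome". The last paragraph on Aim 4 makes the numbered analyses the focus of the aim. The introduction to Aim 4 calls it exploratory.

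**The concern.** Randomisation protects the path from intervention to parent behaviour. It does not protect the path from parent behaviour to child outcome, which is an observational association within arms. When both are taken from the same months, or the parent average runs to the day the child is tested, the association can arise because a child who communicates more draws more strategy use from the parent.

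At stake is the answer to the question the SAP sets for Aim 4: how the intervention works. The condition that Aim 4 follows an Aim 1 or Aim 3 effect is no safeguard. A working intervention combined with child-to-parent influence is exactly the setting in which the false indirect effect appears.

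**Working it through.** **1. Timing, analysis by analysis (SAP, Aim 4 analytic plan).**

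| Analysis | Mediator | Outcome | Order |
|---|---|---|---|
| 4.1a | parent factor, 12-18 mo | child slope, 12-18 mo | same months |
| 4.2a | parent factor, 18-36 mo | word slope, 18-36 mo | same months |
| 4.1b | parent factor, 12-18 mo | CSBS at 18 mo | window ends at outcome |
| 4.2b | parent factor, 18-36 mo | PLS-5 at 36 mo | window ends at outcome |
| 4.3a, 4.3b | child slope, 12-18 mo | word slope 18-36 mo; PLS-5 at 36 mo | mediator first |

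None of the lagged, continuous-time or ALT models is assigned to 4.1 or 4.2. The ALT text names only cross-paths from parent to child (the figure is not available). The SAP's Covariates list contains neither earlier parent use nor earlier child communication.

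**2. The plan's nearest figure.** No power or error rate is given for Aim 4. For main effects at n = 86 the SAP states 80% power at d = .61 and 90% at d = .71. A two-sample t-test (43 per arm and two-sided 0.05, both assumed) gives 79.8% and 90.2%, so these figures reproduce. I use n = 86 below.

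**3. Illustration with no parent effect on the child.** All effect sizes are assumptions. X is intervention (0/1) and t runs from 0 to 1 in T monthly steps (T = 6 or 18).

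- Child: level = L + S·t, with L ~ N(0,1), S ~ N(0.6X, 1) and measurement SD 0.5.
- Parent in month j: P0 + 1.0·X + k·(child level in month j-1) + error, with P0 ~ N(0,1) and error SD 0.5.
- Mediator M: mean of months 1 to T.
- False mediation: both a (M on X) and b (outcome on M, given X) significant at 5%.

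The parent does not enter the child's equation, so the true b is 0. For the same-window slope, with t̄ = (T-1)/(2T):

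a = 1 + 0.6·k·t̄ and b = k·t̄ / [1 + k²(1 + t̄²) + 0.25/T]

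At k = 0.5:

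- T = 6: t̄ = 5/12 = .417; a = 1.125; b = .2083/1.335 = .156; ab = .176, which is 29% of the total effect 0.6.
- T = 18: t̄ = 17/36 = .472; a = 1.142; b = .2361/1.320 = .179; ab = .204, which is 34%.

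The simulation (1,500 trials per cell) gave ab = .176 and .202. Share of trials declaring mediation, 12-18 / 18-36 month window:

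| k | Slope (4.1a / 4.2a) | Endpoint, baseline child score adjusted (4.1b / 4.2b) | Early parent months, later slope |
|---|---|---|---|
| 0 | 4.9% / 5.1% | 5.3% / 5.0% | 5.7% / 5.1% |
| 0.25 | 12.7% / 17.6% | 21.3% / 24.8% | 5.5% / 4.9% |
| 0.5 | 31.1% / 43.0% | 61.0% / 67.6% | 6.1% / 8.3% |
| 1.0 | 61.5% / 77.0% | 96.2% / 96.9% | 6.5% / 14.1% |

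**4. Does baseline adjustment cure it?** The endpoint column is already adjusted and stays far above 5%. A separate check assumed an intervention effect of .8 SD on parent use, a baseline-to-window correlation of .7, and child-to-parent influence of .2, .3 and .5 SD. Adjusting for baseline child level cut same-window false positives from 28%, 58% and 93% to 13%, 26% and 66%. That is a real reduction but not a cure.

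**5. A remedy to avoid.** If parent use over T1-T7 mediates T24 outcomes, adjusting for child level at T7 conditions on the mediated path. With genuine mediation through T7 skills (parent-to-T7 effect .3, .5, .7), power was 40%, 82% and 97% without that adjustment and 5%, 5% and 6% with it.

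**Limits.** These runs use two-stage regression and joint significance, not the SAP's simultaneous SEM with likelihood-based intervals. The full ALT model, and an endpoint analysis with a shortened parent window, were not simulated.

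**The case against.** The best defence is that the SAP does plan for time order. It describes lagged, continuous-time and ALT models, presents them as ways to test its main hypotheses, and promises covariates in both the cross-sectional and longitudinal versions. The sentence about cross-sectional methods also covers 4.3a, whose mediator clearly comes first, so it describes a structure of one predictor, one mediator and one outcome rather than simultaneous measurement.

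This is right about the sentence. The timing problem rests on the definitions of the analyses, not on that sentence, which in any case does not mention 4.1b or 4.2b. The defence does not close the gap: no numbered analysis in 4.1 or 4.2 is tied to a lagged model, and the numbered analyses carry the aim.

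Two stronger readings are tempting and unsupported. First, a reader might infer that 4.2b measures its outcome over the same months as its mediator. It does not: the outcome is one PLS-5 score at 36 months, and 4.1b has the same form. Second, a reader might infer that reverse influence is built into the parent coding in SAP Table 1. The contingent-response and expansion items are percentages of child communication, so they do not rise mechanically when the child communicates more. The language sample is also a separate procedure in which the parent does not talk (protocol, Table 1). Behavioural influence remains possible, and the item on the share of adult communication that responds to the child could rise with child output.

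**Conclusion.** The concern stands in limited form. In 4.1a and 4.2a mediator and outcome share the same months with no lag. In 4.1b and 4.2b the mediator window runs to the outcome date. Both conflict with the SAP's own principle of temporal order.

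A false mediation finding could follow; the documents do not show that it would. It needs real child-to-parent influence, whose strength they do not give, and an intervention effect on parent use. Under the assumptions above, k from 0.25 to 0.5 gives 13-43% for the slope analyses and 21-68% for the endpoint analyses, against 5% at k = 0. Direction and mechanism are secure; the exact rates are not.

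A reader might also infer that the trial's efficacy conclusions are affected. They are not: Aims 1 and 3 do not use these models, and Aim 4 is exploratory. The change should be made, but it is not critical to the trial's main results.

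**What to change.** - **4.1a and 4.2a:** name the cross-lagged/ALT model already in the SAP as the decision model, with autoregressive paths and explicit child-to-parent as well as parent-to-child cross-paths.
- **4.1b and 4.2b:** use parent-strategy months that end before the outcome assessment, and adjust for parent use and child level measured before the mediator window starts.
- Label the same-window versions descriptive.
- **Optional addition:** the T1-T7 parent factor as mediator of T7-T24 word growth and T24 PLS-5, adjusted for T0 parent use and T0 child level but not T7 child level. It should not replace 4.2, which asks about parent use after the intervention.
- Correct the Aim 4 introduction, which gives the 12-18 month mediator to 4.1a and 4.2b where the analytic plan implies 4.1a and 4.1b.

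**Cost:** SAP wording only, since parent-child interactions are already recorded monthly. The price is a more complex model and somewhat lower precision for an exploratory aim. Separation reduces the bias but does not abolish it: under strong influence (k = 1.0) the 18-36 month rate was still 14%.

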Covariates. Controlling for covariates is an important part of any analysis. While randomization and stratification should remove effects of these variables, additional statistical control curtails potential unhappy randomizations and other threats to internal validity. As such, we will examine differences between experimental conditions for the following variables: non-verbal cognitive skills, degree of hearing loss in the better ear, hearing age, hours of hearing device use, SES, sign exposure in the home, other spoken languages in the home and amount of community-based early intervention therapy services. Should a difference exist at any point in the study, we will include that variable in all statistical analyses.

Multiple testing. Our proposed analyses and rich multivariate data collection will allow us to test hypotheses in multiple ways. Our focus on SEM will allow for complex hypotheses to be tested with a single model, obviating part of the need for multiple testing corrections. However, we will further employ Benjamini-Hochberg corrections⁸⁸ as needed to correct for multiple testing. This procedure is a more sophisticated alternative to traditional Bonferroni corrections that better account for multiple simultaneous significant parameters.

[figure not shown]
Aim 1 Analyses

This aim tests the main effects of the intervention, both on parental use of communication support strategies and on child prelinguistic skills. We predict that: (a) parents in the intervention group will use more communication support strategies during intervention than parents in the control group (analysis 1.1); (b) children in the intervention group will have greater growth in rate of prelinguistic communicative acts between 12 months (pre) and 18 months of age (post) (analysis 1.2a) and greater overall prelinguistic skills at 18 months of age (post) (analysis 1.2b) than children in the control group. We will employ a mix of traditional and advanced statistical methods, balancing simplicity of linear regression and related methods with sophisticated SEMs that handle attrition and missing data and allow for more flexible integration of time-varying covariates.

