One example of a latent growth curve model is shown in Figure 2, where latent intercepts (level) and slopes (indicated by the circles labeled " L_c " and " S_c ") represent unmeasured variables that describe how children differ from each other in their overall level of prelinguistic development. These two latent variables predict and describe how children grow in their prelinguistic communicative abilities from age 12 months (C_{12}) to age 18 months (C_{18}). Latent growth models will be used for analyses 1.1 and 1.2a, all of which use a slope factor as a dependent variable.

Aim 1 analytic plan. Analyses for Aim 1 will utilize SEM equivalencies of both traditional regressions and growth curve extensions of these models. We will estimate all models in SEM to minimize the impact of attrition.

Analysis 1.1. Intervention will predict the slope factor in a latent growth curve model of overall parent use of communication support strategies, which is a latent variable of parent use of communication support strategies estimated monthly from 12 months (pre) to 18 months of age (post). This will utilize the CUFFS method (McArdle, 1988) of estimating growth in latent variables.

Analysis 1.2a. Intervention will predict the slope factor in a latent growth curve model of child prelinguistic communicative acts from a language sample from 12 months (pre) to 18 months of age (post). This will be accomplished by including intervention as a predictor in the child prelinguistic communicative acts growth curve.

Analysis 1.2b. CSBS Total Scaled Scores at 18 months of age (post) will be regressed on intervention status controlling for CSBS Total Scaled Scores at pre-test and other relevant covariates.

Aim 2 Analyses

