Power for tests of intervention effects were estimated using G*Power⁹⁵ supplemented with custom simulations to verify accuracy and tailor assumptions to our research design. Given a sample size of 86 (96 recruited participants with 10% attrition), we project greater than 99% power for main effects of the intervention (aim 1) as large as those shown in our pilot study (d=1.07) (see Justification and Feasibility in Research Strategy). We further project 80% power for effects as low as d=.61 and 90% for d=.71. Each of the three previous estimates assume control for pre-test and 10% attrition (e.g., n=86). Our research group has maintained greater than 95% retention in comparable studies over the last two years. We would retain power for smaller effect sizes of d=.58 (80% power, down from d=.61) and d=.67 (90% power, down from d=.71) if no attrition occurs.

The above power analysis covers the primary analyses for Aims 1 and 3. However, these aims also include growth in parent and child outcomes assessed monthly. These analyses depend on latent growth curve models, as described above and require a simulation-based power estimate, as described in Zhang & Wang (2009). We simulated our monthly assessments four thousand times, varying our predicted effect size and distribution of latent intercepts and slopes. This simulation yielded reliable power estimates for each effect size. The use of longitudinal data yield improved power over our simple pre-test-post-test designs in the previous paragraph. We project 80% power for d=.34, and 90% for d=.45. Furthermore, we have 80% power to detect moderators (aim 2) that account for 7.8% of variance in the outcome or greater, and 90% for 10.4% of variance. In summary, this study is well-powered to test the effects of intervention on parent and child outcomes.

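### The Aim 4 mediation models do not specify adjustment for T0 parent strategy use or the T0 child outcome, which leaves the non-randomised mediator-to-outcome path open to baseline confounding

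*SAP*

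**What the plan says.** The SAP's Aim 4 analytic plan sets out six mediation models.

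- **4.1b, 4.2b and 4.3b** are chains from intervention to a latent mediator to one observed score. For 4.1b: "This latent parent strategy variable will in turn predict CSBS Total Scaled scores at 18 months of age (post". 4.2b and 4.3b end in the PLS-5 at 36 months. None names a T0 score.
- **4.1a, 4.2a and 4.3a** end in a growth slope. The SAP says of them: "These approaches will use basic cross-sectional methods with single variables representing the predictor, mediator, and outcome". It adds that the mediators and outcomes are estimated within growth curves.
- **The parent mediator** (4.1a, 4.1b, 4.2a, 4.2b) is overall strategy use across a window. No model names its T0 value as a covariate. In 4.3a and 4.3b the mediator is the child's prelinguistic slope.

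Two statements govern covariates. Under Longitudinal mediation: "we will include relevant covariates in all steps of both the cross-sectional and longitudinal mediation models". Under Covariates, the SAP lists eight background variables, none of them T0 strategy use or a T0 language score, with the rule "Should a difference exist at any point in the study, we will include that variable in all statistical analyses".

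By contrast, Analysis 1.2b regresses post-intervention CSBS on arm "controlling for CSBS Total Scaled Scores at pre-test and other relevant covariates", and Analysis 3.2b handles the PLS-5 pre-test in the same way.

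**The concern.** Randomisation makes the intervention-to-mediator path (a) a fair comparison. It does nothing for the mediator-to-outcome path (b), which compares families by how much strategy use they show. A parent who was already responsive at T0 will tend to score high later, and a child who was already communicating well will tend to score high later. If these two T0 features are correlated, b is non-zero with no causal effect behind it. Multiplied by a real effect on parents, that yields an apparent indirect effect.

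The rule in the Covariates section cannot catch this. It is triggered by a difference between arms, whereas confounding of b exists when the arms are perfectly balanced. The pre-test is therefore named where randomisation already protects the comparison (1.2b, 3.2b) and left unnamed where nothing else does. At stake is the claim about how the intervention works.

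**Working it through.** **Inputs from the SAP (Power Analysis).** "Given a sample size of 86 (96 recruited participants with 10% attrition"); "main effects of the intervention (aim 1) as large as those shown in our pilot study (d=1.07"); and "We further project 80% power for effects as low as d=.61 and 90% for d=.71". The SAP gives no power figure for mediation.

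**The plan's own figures.** A two-sided two-sample t test, with alpha .05 and 1:1 allocation assumed, gives for 43 per arm 99.8% power at d = 1.07, 79.8% at .61 and 90.2% at .71. For 48 per arm it gives 80.3% at .58 and 90.1% at .67. All match the SAP, so n = 86, with a = 0.61 and 1.07 as plausible sizes for the first path, is a fair basis. Using these d values for path a is an assumption: the SAP does not tie the pilot effect to parent strategy use.

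**Model for the observed end-point structure (as in 4.1b).** X is arm; within-arm SDs are 1 when b = 0; ρ is the T0 correlation between parent use M0 and child score Y0; s is the stability of each measure.

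- M = aX + sM0 + error
- Y = bM + sY0 + error

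Without T0 terms, the fitted b tends to b + ρs², so the indirect effect is biased by aρs². With true b = 0:

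| ρ / s | ρs² | bias, a = 0.61 | bias, a = 1.07 |
|---|---|---|---|
| .2 / .4 | .032 | .02 SD | .03 SD |
| .3 / .5 | .075 | .05 SD | .08 SD |
| .4 / .6 | .144 | .09 SD | .15 SD |
| .5 / .7 | .245 | .15 SD | .26 SD |

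A simulation of 1,000,000 subjects agrees with these to within .01 SD. With both T0 values in the model, the bias is about 0. With a = 0 the mean indirect effect is about 0 either way.

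**False-mediation rate.** 3,000 simulated trials per setting, n = 86, true b = 0. Joint significance of a and b stands in for the SAP's likelihood-based interval, and least squares on observed variables for the SEM. Monte Carlo error near 5% is √(.05 × .95 / 3000) ≈ 0.4 points.

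| ρ / s | no T0 terms, a = 0.61 | no T0 terms, a = 1.07 | both T0 values, a = 0.61 | both T0 values, a = 1.07 |
|---|---|---|---|---|
| .2 / .4 | 4.7% | 5.8% | 4.2% | 4.7% |
| .3 / .5 | 8.3% | 10.2% | 4.2% | 4.7% |
| .4 / .6 | 20.2% | 25.3% | 4.3% | 4.7% |
| .5 / .7 | 49.6% | 61.2% | 4.6% | 4.7% |

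In this model the T0 outcome alone also restores the rate (3.9% to 5.1%), because M0 reaches Y only through its correlation with Y0. If T0 parent style also acts on the later child score by another route, M0 is needed as well.

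**Slope outcome (as in 4.1a).** A separate unadjusted simulation at n = 86, a = 1.0 and true b = 0, with assumed variances, gave 4.7% to 6.3% when the child's intercept and slope were uncorrelated. It gave 5% to 11% when they correlated at ±.3, with a negative spurious b at −.3.

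**The case against.** A reader might infer that the plan leaves T0 values out. The text does not go that far. The mediation section promises relevant covariates in every step, and Analysis 1.2b's wording, which speaks of the pre-test and other relevant covariates, treats the pre-test as one of them. If that reading holds for 4.1b, 4.2b and 4.3b, the T0 outcome is in the model, and under the simple model above most of the problem disappears. This stands as a reason to call the defect one of specification. It does not settle the matter, since nothing in the SAP names T0 parent use as a covariate.

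A reader might also infer that the untreated T0 sample is averaged into the parent mediator in 4.1a and 4.1b. The stated window does open at pre. But SAP Table 1 counts 6 occasions between pre and post and 18 from post to follow-up; 6 + 18 = 24 matches the protocol's T1 to T24 and would leave T0 out. The point is ambiguous and matters little: with T0 as one of seven averaged occasions, the spurious effect is .09 SD against .08 SD (ρ = .3, s = .5, a = 1.07).

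Third, the growth models handle starting level in part. 4.1a has a latent intercept at pre, and 4.3a lets growth parameters correlate. This stands only in part. The SAP does not say that the slope is regressed on its intercept, a free correlation is not conditioning, and the spoken-word curves in 4.2a and 4.3a start after treatment. The SAP also describes an autoregressive latent trajectory model, but it assigns the three slope analyses to the cross-sectional form.

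Finally, Aim 4 is labelled exploratory. That limits the consequence. The reason given, however, is that Aim 4 depends on an effect in Aim 1 or Aim 3, so it will be read mainly when path a is likely to be non-zero, which is when the bias operates.

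**Conclusion.** The concern holds as a gap in specification. Analyses 4.1b, 4.2b and 4.3b do not specify adjustment for the T0 outcome, and 4.1a, 4.1b, 4.2a and 4.2b do not specify adjustment for T0 parent strategy use; the general covariate wording does not close the gap.

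Its size is uncertain. The documents give no T0 correlation or stability, so the range from essentially no inflation to more than half of null trials reflects assumptions, not estimates. The middle setting roughly doubles the nominal rate. It would be wrong to read the high figures as applying to all six models: they describe an observed end-point with a parent mediator, and the slope-outcome check gave much smaller inflation. Nor do they touch the Aim 1 and Aim 3 conclusions, which rest on the randomised comparison.

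**What to change.** Name the baseline terms in each Aim 4 model:

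- **4.1b and 4.2b:** enter T0 parent strategy use and the T0 outcome score (CSBS or PLS-5) in both the mediator and the outcome equation.
- **4.3b:** enter T0 PLS-5 and condition on the latent intercept of the prelinguistic curve.
- **4.1a:** enter T0 parent use and regress the child slope on its latent intercept. Do not add T0 communicative acts separately, because they already indicate that curve and would be both its cause and its effect.
- **4.2a:** enter T0 parent use and T0 spoken words, since the word curve starts after treatment.
- **4.3a:** condition on the prelinguistic intercept and on T0 spoken words.

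State also that the parent mediator in 4.1a and 4.1b is built from T1 onward, with T0 used only as a covariate, and that these terms enter whether or not the arms differ.

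The cost is SAP wording and a few degrees of freedom. The protocol's assessment table already schedules the CSBS, PLS-5, language sample, parent-child interaction and MCDI at T0.
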